Consequently, the primary study, as outlined in the original trial registration, aiming to use ultrasound speckle tracking (STU) to monitor muscle contractility in multiple sclerosis (MS) patients receiving vs. not receiving fampridine, as well as to relate these results to performance-based measures and biomarkers to explore disease progression and muscle activity, has been cancelled. The following pages outline the statistical analysis plan regarding four exploratory studies that originate from the initial trial registration but with a revised aim, outcome measures, and time points.

Study 1

Objective

To investigate whether Speckle Tracking Ultrasonography (STU) can quantitatively evaluate muscle function in participants with MS, by means of correlations to conventional clinical assessments.

Participants

The participants who performed STU analyses at baseline.

Outcome measures

Demographic measures – at baseline

- Age
- Gender
- Expanded Disability Status Score (EDSS) [1]
- Multiple Sclerosis Impairment Scale (MSIS) [2]
- Disease duration
- Sub-diagnosis (MS)
- Medical treatment (MS)

- Walking aids
- Muscle strain of the Soleus muscle (SOL), at different percentages of Maximal Voluntary Contractions (%MVC) – baseline data:
 - SOL20 (20 %MVC)
 - SOL40 (40 %MVC)
 - SOL60 (60 %MVC)
- Muscle strain of the Biceps muscle (BB), at different %MVC – baseline data
 - BB20 (20 %MVC)
 - BB40 (40 %MVC)
 - BB60 (60 %MVC)
- Muscle strain of the Supraspinatus muscle (SS) at different %MVC – baseline data
 - SS40 (40 %MVC)
 - SS60 (60 %MVC)
 - SS80 (80 %MVC)
- Clinical performance tests, legs – baseline data
 - The Timed 25-Foot Walk (T25FW) [3]
 - The Six Spot Step Test (SSST) [4]
 - 2-minute Walk Test (2MWT) [5]
 - 12-Item MS Walking Scale (MSWS-12) [6].
- Clinical performance tests, arms – baseline data
 - 9-Hole Peg Test (9HPT) [7]
 - Oxford Shoulder Score (OSS) [8]

Statistical analysis

Descriptive statistics – baseline data

- Gaussian distribution will be inspected by normal probability plots and the Shapiro-Wilk test.
- Data will be reported as numbers (n) and percentage (%), mean values and standard deviations (SD), and/or median values and interquartile range (IQR), as required, according to assumption of Gaussian distribution.

Criterion validity – baseline data

- Non-bilaterally tests: STU test-side will be used for analyses.
- The Timed 25-Foot Walk Test (T25FW) is appointed gold standard for leg function.
- 9-Hole Peg Test (9HPT) is appointed gold standard for arm function.
- Criterion validity of strain and clinical performance tests will be performed as follows:
 - Normality and assumptions will be examined by means of scatterplots and linear regressions for strain and clinical performance test using gold standards as the dependant variables.

- Correlations between gold standards and strain will be assessed using Pearson's product-moment correlation coefficient r and/or Spearman's rank-order correlation coefficient ρ (rho).
- Correlations between gold standards and clinical performance tests will be assessed using Pearson's product-moment correlation coefficient r and/or Spearman's rank-order correlation coefficient ρ (rho).

Comparisons of criterion validity – baseline data

- For comparisons of criterion validity, we will use the results of the Spearman's rank-order correlation coefficient ρ (rho). This to ensure that the parameters are the same for all comparisons.
- Bootstrapping will be performed because independence cannot be expected, between correlation estimates from the same patient.
- Difference between criterion validity will be assessed using squared correlations on Fischer's Z-scale in combination with bootstrapping to define accelerated Bootstrap Confidence Intervals (95% BCa CI).

Study 2

Objective: To test the hypothesis that quality of gait using Gait Profile Score (GPS) based on nine different Gait Deviation Scores (GVS), as well as gait function using performance-based tests, spatiotemporal parameters, and self-perceived gait function, will improve in MS patients following two weeks of treatment with Fampridine. In addition, we hypothesize that changes in GPS are positively associated with changes in performance-based measures.

Participants

- A subgroup of participants, randomly allocated 3-dimensional gait analysis (3DGA).
- Age-matched reference group consisting of healthy people, collected in our own lab.

Outcome measures

- Demographic measures – at baseline
 - Age
 - Gender
 - Height and weight (from which Body Mass Index (BMI) was calculated)
 - Disease duration
 - EDSS [1]
 - Walking aids
- Gait Quality according to Baker et al 2009 [9] – baseline and change between baseline and 14-days follow-up
 - Gait Profile Score (GPS)
 - Gait Variable Scores (GVS)
 - Pelvic tilt
 - Pelvic obliquity

- Pelvic rotation
 - Hip flexion-extension
 - Hip abduction-adduction
 - Hip rotation
 - Knee flexion-extension
 - Ankle dorsi-/plantar flexion
 - Foot progression
- Clinical performance based tests – baseline and change between baseline and 14-days follow-up
 - T25FW [3]
 - SSST [4]
 - 2MWT [5]
 - MSWS-12 [6]
 - Spatiotemporal parameters

Statistical analysis

A priori sample size calculation

Sample size calculation was performed using GPS values formerly reported on MS patients (GPS mean \pm SD) 9.1 ± 1.3 [10] and the minimal important difference of 1.6 GPS defined by Baker et al. 2009 [9]. The SD of 1.3 from the MS population [10] was used since no SD was reported by Baker et al. 2009 [9]. A minimum of nine participants was found to be needed, based on a paired design, alpha of 0.05, statistical power of 80%, assumption of normal distribution of data.

Descriptive statistics – baseline data

- Gaussian distribution will be inspected by normal probability plots and the Shapiro-Wilk test.
- Data will be reported as numbers (n) and percentage (%), mean values and standard deviations (SD), and median values and interquartile range (IQR), as required, according to assumption of Gaussian distribution.
- Comparison of characteristics of included MS patients and patients randomised to perform 3DGA, but declined to perform the 3DGA, will be explored using Student's unpaired *t*-test (parametric) and Wilcoxon rank sum test (non-parametric)

Changes between baseline and 14-days follow-up

- Results according to kinematic and spatiotemporal data will be reported for the participant's dominant side.
- Gaussian distribution will be inspected by normal probability plots and the Shapiro-Wilk test.
- Change will be examined using Student's paired *t*-test (parametric) and Wilcoxon signed rank test with median values (non-parametric).
- Due to the low number of participants required, bootstrap confidence intervals (95% BCa CI) can be relevant for the non-parametric analysis.

Correlations of change between baseline and 14-days follow-up

- Correlations between change in GPS and change in performance-based tests will be examined using Pearson's product-moment correlation coefficient *r* and/or Spearman's rank-order correlation coefficient ρ (rho).

Study 3

Objective

To assess potential changes of relevant biomarkers in participants with MS following two weeks of Fampridine treatment. Furthermore, to explore the correlation between biomarkers and clinical performance measures.

Participants

The group of participants, who provided a blood sample at baseline

Outcome measures

- Demographic measures – at baseline
 - Age
 - Gender
 - Expanded Disability Status Score (EDSS) [1]
 - Multiple Sclerosis Impairment Scale (MSIS) [2]
 - Disease duration
 - Sub-diagnosis (MS)
 - Medical treatment (MS)
 - Walking aids
 - Smoking status
 - Alcohol intake

- Biomarkers – change/baseline
 - Plasma IFN-gamma (pg/mL)
 - Plasma IL-2 (pg/mL)
 - Plasma IL-4 (pg/mL)
 - Plasma IL-8 (pg/mL)
 - Plasma IL-17 (pg/ml)
 - Plasma TNF (pg/mL)
 - Plasma TNF-RI (pg/mL)
 - Plasma TNF-RII (pg/mL)
 - Neurofilament light chain (NF-L)
 - Glial fibrillary acidic protein (GFAP)

- Clinical measures – change/baseline
 - T25FW [3]
 - SSST [4]
 - 2MWT [5]
 - MSWS-12 [6]
 - 9HPT [7]
 - OSS [8]
 - STU

Statistical analysis

Descriptive statistics – baseline data

- Gaussian distribution will be inspected by normal probability plots and the Shapiro-Wilk test.
- Data will be reported as numbers (n) and percentage (%) or mean values and standard deviations (SD), and median values and interquartile range (IQR), as required, according to assumption of Gaussian distribution.

Changes between baseline and 14-days follow-up

- Gaussian distribution will be inspected by normal probability plots and the Shapiro-Wilk test.
- Change will be examined using Student's paired *t*-test (parametric) and Wilcoxon signed rank test with median values (non-parametric).

Correlations of change between baseline and 14-days follow-up

- If a change in biomarkers is demonstrated, correlations between change in biomarkers and change in clinical measures will be examined using Pearson's product-moment correlation coefficient *r* and/or Spearman's rank-order correlation coefficient ρ (rho).
- If no change in biomarkers is demonstrated, correlations between baseline data for biomarkers and baseline data for clinical measures will be examined using Pearson's product-moment correlation coefficient *r* and/or Spearman's rank-order correlation coefficient ρ (rho).

Study 4

Objective

To evaluate changes in hand and walking parameters in participants with MS following Fampridine treatment, according to the disability level.

Participants

Participants, who completed both baseline and 14-days follow-up, who followed instructions of Fampridine intake, and who did not receive Fampridine at inclusion.

Outcome measures

- Demographic measures – at baseline
 - Age
 - Gender
 - EDSS [1]
 - Disease duration
 - Sub-diagnosis (MS)
- Clinical measures – baseline and change between baseline and 14-days follow-up
 - T25FW [3]
 - SSST [4]
 - 2MWT [5]
 - MSWS-12 [6]
 - 9HPT [7]

Statistical analysis

Descriptive statistics – baseline data

- Gaussian distribution will be inspected by normal probability plots and the Shapiro-Wilk test.
- Data will be reported as numbers (n) and percentage (%), mean values and standard deviations (SD) and median values and interquartile range (IQR), as required according to assumption of Gaussian distribution.

Definition of subgroups according to their EDSS

- Subgroup 1: Moderate walking disability (EDSS 4.5-5.5)
- Subgroup 2: Severe walking disability (EDSS 6.0-7.0)
- Comparison of subgroups at baseline will be examined using Student's unpaired *t* test (parametric) and Wilcoxon rank sum test/Mann Whitney test (non-parametric).

Changes between baseline and 14-days follow-up

- Gaussian distribution will be inspected by normal probability plots and the Shapiro-Wilk test.
- Change for all included participants, subgroup 1 and subgroup 2, respectively, will be examined using Student's paired *t*-test (parametric) and Wilcoxon rank sum test (non-parametric).
- Comparison of change scores between subgroups will be examined using Student's unpaired *t* test (parametric) and Wilcoxon rank sum test/Mann Whitney test (non-parametric).

References

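### Does comparing squared correlations in Study 1 let a strain measure that runs the wrong way pass as valid?

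*SAP*

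**What the plan says.** Study 1 asks whether speckle tracking ultrasonography (STU) "can quantitatively evaluate muscle function in participants with MS, by means of correlations to conventional clinical assessments". Its sample is described as follows: "The participants who performed STU analyses at baseline".

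The analysis has two steps.

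- **Criterion validity – baseline data.** The gold standard for legs is named: "The Timed 25-Foot Walk Test (T25FW) is appointed gold standard for leg function". The 9-Hole Peg Test (9HPT) has the same role for arms. After scatterplots and linear regressions comes the strain analysis: "Correlations between gold standards and strain will be assessed using" Pearson's r and/or Spearman's rho. The clinical tests are treated in the same way. These coefficients are not squared.
- **Comparisons of criterion validity – baseline data.** Here "we will use the results of the Spearman's rank-order correlation coefficient ρ (rho"). Then: "Difference between criterion validity will be assessed using squared correlations on Fischer's Z-scale in combination with bootstrapping", with 95% BCa intervals.

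Study 1 states no expected sign for strain. The Study 2 objective does state a direction: "we hypothesize that changes in GPS are positively associated with changes in performance-based measures". The SAP introduces all four as "four exploratory studies that originate from the initial trial registration".

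**The concern.** A squared correlation has no sign. If strain related to the gold standard at −rho in the unexpected direction, and a clinical test related to it at +rho in the expected direction, the comparison would put the true difference at 0. A measure of muscle function should move the right way as well as move strongly, so an interval around 0 might be read in strain's favour.

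There is a second, technical worry. The squared statistic is flat at 0, so the comparison may struggle to separate a strain measure with no relation to the gold standard from a modestly valid test. If both effects mattered to the conclusions, Study 1 could overstate what STU can do.

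**Working it through.** **Inputs.** From the SAP: Spearman's rho, squared, on Fisher's Z scale, with a 95% BCa bootstrap interval; and a cohort of 48 (Administrative Information), which is an upper bound for Study 1. The SAP gives no sample size, power or expected correlation for Study 1, so there is no figure to reproduce. All correlations below are assumptions, and n=30 is an assumed smaller STU subset.

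**1. Is the comparison blind to sign?** Write s for strain and t for the clinical test.

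- Squared scale: d = atanh(ρs²) − atanh(ρt²)
- Signed scale: d = atanh(ρs) − atanh(ρt)

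For equal strength in opposite directions:

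| Absolute rho | atanh(rho²), either sign | Squared d | Absolute signed d = 2·atanh(rho) |
|---|---|---|---|
| 0.3 | 0.0902 | 0 | 0.619 |
| 0.5 | 0.2554 | 0 | 1.099 |
| 0.7 | 0.5361 | 0 | 1.735 |

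So yes, this step cannot see the sign. The slope of atanh(ρ²) is 2ρ/(1 − ρ⁴), which is 0 at ρ = 0, so the flatness is real too.

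**2. Is the sign lost to the analysis?** No. The preceding step assesses the unsquared coefficient of strain with the same gold standard, and the comparison draws on those Spearman results. A strain measure at −0.4 appears there as −0.4. At n=48 its own rho, tested at two-sided 5%, would be significant in 80.2% of data sets at an absolute value of 0.4 and in 27.4% at 0.2.

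**3. What does squaring do to the results?** Trivariate normal data, patients resampled, BCa with jackknife acceleration, 4000 data sets of 1000 resamples each (Monte Carlo SE at most 0.8 points). The two measures correlate only through the gold standard unless stated. Entries are the percentage of intervals that exclude 0.

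| Strain vs test | n | Squared | Signed |
|---|---|---|---|
| −0.4 vs +0.4 | 48 | 7.3 | 96.6 |
| −0.4 vs +0.4 | 30 | 6.9 | 83.0 |
| −0.2 vs +0.2 | 48 | 4.3 | 47.3 |
| 0 vs 0 | 48 | 0.7 | 5.4 |
| 0 vs 0.3 | 48 | 12.9 | 29.4 |
| 0 vs 0.5 | 48 | 59.5 | 69.7 |
| 0 vs 0.5, measures correlate 0.3 | 48 | 60.2 | 85.9 |
| 0.1 vs 0.5 | 48 | 55.7 | 55.6 |
| 0.2 vs 0.5 | 48 | 41.3 | 37.4 |
| 0.2 vs 0.7 | 48 | 88.3 | 86.4 |
| 0 vs 0.7 | 48 | 96.8 | 97.9 |
| 0 vs 0.5 | 30 | 32.2 | 47.9 |
| 0.2 vs 0.5 | 30 | 23.6 | 23.5 |

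The first three rows are not lost power. On the squared scale the true difference is 0, so a rate near 5% is the right answer to the question of strength. The signed column answers another question.

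The other rows are mixed. Squaring loses when strain is at or very near 0 and the test is weak to moderate. It is level or slightly ahead once strain has some validity or the test is strong. With both correlations at 0 it errs on the cautious side. Undercoverage is small: the worst case is 91.8% (0.1 vs 0.3, n=48), against 95.2% on the signed scale.

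**4. What would a signed comparison need?** A direction for up to nine strain measures: three muscles at three contraction levels each. If a direction is declared wrongly, two measures of equal strength 0.4 are analysed as −0.4 against +0.4. The 96.6% in the first row then becomes the rate of spurious differences.

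**The case for a change.** The best case for a change is that criterion validity depends on direction and that the sign is visible earlier but has no declared expectation to be read against. Data collection ended in October 2021 and the SAP is dated March 2022, so a direction chosen once rho is seen would be post hoc. Orienting every measure so that higher means better would deal with times and distances without discarding the sign. Study 2 shows that the authors can state a direction. In some settings the power loss is also real, as at 0 vs 0.5 with extra correlation between the measures.

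Part of this stands. Squaring is sign-blind, Study 1 declares no direction, and power does fall in one region. The rest is weaker than it looks.

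- Strain is taken at fixed percentages of maximal voluntary contraction, and the SAP offers no ground for an expected sign for any of the nine measures. Where no direction can be justified, the alternative falls back on the squared comparison beside the signed rho, which is essentially what the SAP already yields.
- Study 2 is framed as a hypothesis test, whereas Study 1 asks whether STU can work at all. Study 2's positive association also covers a timed walk and a walk of fixed duration without orienting them, so it is no model for specifying direction.
- The SAP does not name the pairs to be compared. It is likely, but not stated, that this step sets strain against the clinical tests.
- Nothing in the SAP makes the region where squaring loses more plausible than the region where it is level or ahead.

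**Conclusion.** The concern does not hold. The comparison asks how strongly each measure is related to the gold standard. That is a coherent question when, as the test names imply, one test is a time over a fixed distance and another a distance over a fixed time, so that equally good tests carry opposite signs. Direction is answered by the signed coefficients one step earlier. The harm arises only if the comparison is read alone and an interval including 0 is taken as proof of equal validity, and the SAP asks for neither.

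The contrast of 7.3% with 96.6% is a difference between two estimands and not an error rate. The power effects run from a loss of 16.5 points (29.4 − 12.9, at 0 vs 0.3) to a gain of 3.9 points (41.3 − 37.4, at 0.2 vs 0.5) at n=48 when the measures correlate only through the gold standard. The loss grows to 25.7 points (85.9 − 60.2, at 0 vs 0.5) if they correlate 0.3. All of this rests on assumed correlations and normal data.

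Moving to a signed comparison is a trade-off that a statistician could reasonably refuse. Printing the signed rho beside each squared comparison would help the reader, but that is a matter of presentation. The results are sound if the plan is followed as written.

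### Study 2 gives the small sample as its reason for BCa bootstrap intervals, but that is where BCa is least reliable; an exact interval matched to the estimand should replace it

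*SAP*

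**What the plan says.** In the SAP, Study 2, under the heading on changes between baseline and 14-days follow-up, change is tested with the paired t-test or, as the non-parametric branch, with the "Wilcoxon signed rank test with median values (non-parametric"). The next bullet reads: "Due to the low number of participants required, bootstrap confidence intervals (95% BCa CI) can be relevant for the non-parametric analysis".

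The low number goes back to the a priori sample size calculation of Study 2: "A minimum of nine participants was found to be needed". Its inputs are "the minimal important difference of 1.6 GPS" and an SD taken from another MS sample ("The SD of 1.3 from the MS population [10] was used"), and it is "based on a paired design".

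The SAP does not say which statistic is bootstrapped, with how many resamples, or when the option would be used. The medians in the preceding bullet make the median change the natural reading. No exact interval is mentioned.

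**The concern.** The BCa correction improves on simpler bootstrap intervals as the sample grows; it does not rescue a very small one. With nine changes, a bootstrap median can only be one of the nine observed values. The acceleration term rests on leave-one-out medians that take only three values, all formed from the middle three observations. The interval therefore jumps between a few order statistics, and minor software conventions decide which ones.

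Two things are at stake. Intervals labelled 95% for changes in GPS, the nine GVS, the walking tests and the spatiotemporal parameters may miss the true change more often than 5% of the time. And because a BCa interval for the median does not invert the signed rank test, the interval and the p-value for the same outcome may disagree about whether zero is excluded.

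**Working it through.** **1. The plan's own figure.** Inputs from the SAP: difference 1.6, SD 1.3, alpha 0.05 (two-sided assumed, as the sidedness is not stated), power 80%, paired design.

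- Standardised difference: 1.6/1.3 = 1.231.
- Normal approximation: (1.960 + 0.842)²/1.231² = 5.2, so 6.
- Noncentral t: 8, with power 0.897 at n = 9.
- Divided by the Wilcoxon efficiency: 8/0.955 = 8.4, so 9.

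Nine is reproduced if 1.3 is read as the SD of the within-patient change. It is used below as the planned floor, not as the analysed number.

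**2. BCa for the median at n = 9, by hand.** Write X(k) for the k-th smallest change. A bootstrap median is at or below X(k) when at least 5 of 9 draws come from the k smallest values, with probability P(Bin(9, k/9) ≥ 5):

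| k | 1 | 2 | 3 | 4 | 5 | 6 | 7 | 8 |
|---|---|---|---|---|---|---|---|---|
| Probability | 0.0014 | 0.0304 | 0.1448 | 0.3655 | 0.6345 | 0.8552 | 0.9696 | 0.9986 |

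The bias correction z0 is the normal quantile of the share of bootstrap medians below the sample median X(5). A share of 0.6345 − 0.3655 = 0.269 ties with X(5), so the counting rule matters. The acceleration is at most 0.012 in absolute value here and does not change which order statistics are picked, so the levels are close to Φ(2·z0 ± 1.96). Coverage follows from the number of values below the true median, which is Bin(9, ½) for any continuous distribution.

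- Ties not counted: z0 = −0.344; levels 0.004 and 0.898; interval [X(2), X(7)]; coverage 1 − (10 + 46)/512 = 89.1%.
- Ties counted in full: the mirror image, [X(3), X(8)], also 89.1%.
- Ties counted half (mid-rank): z0 = 0; levels 0.025 and 0.975; interval [X(2), X(8)]; coverage 1 − 20/512 = 96.1%.

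The third case is the limit of unlimited resampling. The level 0.025 lies close to the step at 0.0304, so resampling noise sometimes moves an end inward.

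**3. Simulated coverage of BCa for the median.** Changes were normal, heavy-tailed or skewed, with about 1,000 to 2,000 resamples per interval.

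| n | Coverage |
|---|---|
| 9, ties not counted or counted in full | 88–90% (87–91% across all runs) |
| 9, mid-rank | about 93% (93–95% across all runs) |
| 12 | 92–94% |
| 15 | 90–93% |
| 20 | 93–95% |

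**4. Exact alternatives at n = 9.**

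- Signed rank: of the 512 sign patterns, 10 give a rank sum of 5 or less (1 + 1 + 1 + 2 + 2 + 3). The inverted interval has coverage 1 − 2·10/512 = 96.1% for symmetric changes. The next narrower one has 1 − 2·14/512 = 94.5%.
- Order statistics: [X(2), X(8)] has coverage 1 − 2·(1 + 9)/512 = 96.1% for the median, with no symmetry needed.

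**5. Agreement with the planned test at n = 9.** With no true change, the BCa median interval and the exact signed rank test disagreed about zero in about 5–17% of simulated samples, depending on distribution and tie rule. With a change of 0.8 scale units they disagreed in 16–30% (normal: 19–22%). The inverted signed-rank interval cannot disagree.

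**6. Limits of the alternatives.**

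- The signed-rank interval covered the pseudomedian in about 94–96% of samples, but for skewed changes at n = 20 it covered the raw median in only about 89–93%.
- The order-statistic interval is somewhat wider than BCa. For normal changes the mean widths are 1.58 against 1.33–1.36 at n = 12, and 1.17 against 1.05–1.06 at n = 20.

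**The case against.** The case for leaving the sentence alone has several sound parts.

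- BCa is an option, not a commitment. The specified analysis is the t-test or the signed rank test, and no decision hangs on the interval. The SAP calls all four studies exploratory. This stands and limits the weight of the point.
- Nine is a minimum. A reader might infer that nine patients will be analysed, but the SAP gives no size for the gait-analysis subgroup, only 48 for the whole cohort. At n = 20 the shortfall is 0–2 points.
- A reader might infer that BCa always falls short of 95% at n = 9. It does not: with mid-rank counting it is close to nominal, and with unlimited resamples it is the order-statistic interval itself. That favours specifying the exact interval directly.
- A reader might point to the mean, where simulated BCa coverage at n = 9 is 81–93%. The SAP ties this branch to medians, so those figures do not measure the plan's shortfall.
- The signed-rank interval is not exact in general. Skewness is a likely reason to reach the non-parametric branch, and there the interval does not target the raw median. It can also be wider than mid-rank BCa (2.51 against 2.16 for t-distributed changes with 3 degrees of freedom at n = 9). Tied or zero changes, plausible for MSWS-12, break the exact null distribution. All of this stands, and the fix has to allow for it.

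The objection does not rescue the stated reason: a low number of participants is no argument for BCa.

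**Conclusion.** The point holds as a modest one about interval calibration and agreement with the p-value. The rationale is the wrong way round. At the planned minimum of nine, a BCa interval for the median covers about 88–93% in simulation: 89.1% by direct calculation under two of the three tie rules, and close to nominal under the third. Coverage is 90–93% at n = 15 and 93–95% at n = 20. These figures assume that the median is bootstrapped, that changes are continuous, and that about 1,000 to 2,000 resamples are used.

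A reader might infer that the Study 2 tests or conclusions are invalid. The SAP does not support that: the signed rank test is unaffected and the interval is optional. Nor does the point extend to Study 1, where BCa serves a different quantity and is justified by dependence between correlations. The change is worthwhile but not essential.

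**What to change.** Replace the bootstrap sentence in Study 2 with one of the following, chosen in advance.

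- *When the Wilcoxon signed rank test is used, the change will be reported as the Hodges-Lehmann estimate (pseudomedian) with the 95% confidence interval obtained by inverting that test.* State that it is exact only for symmetric changes without ties.
- If the median is the target: *the median change will be reported with its exact order-statistic (sign-test) 95% confidence interval.*

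In either case, add that outcomes with tied or zero changes, for example MSWS-12, use the tie-handled version.

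The cost is one sentence and standard software output. With the first option, the interval must not be presented as one for the raw median, even if that median is shown beside it. With the second, the interval is somewhat wider than BCa and need not agree with the signed rank p-value.

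### Study 3 lets a test of mean biomarker change decide which correlations are examined, and leaves the trigger for that choice undefined

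*SAP*

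**What the plan says.** The Study 3 objective has two parts: to assess biomarker change over two weeks of fampridine, and "Furthermore, to explore the correlation between biomarkers and clinical performance measures". The second part carries no condition and does not say whether baseline values or changes are meant.

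Biomarker change is tested by a paired t-test or a Wilcoxon signed rank test. The section on correlations of change then has two branches:

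- "If a change in biomarkers is demonstrated, correlations between change in biomarkers and change in clinical measures will be examined"
- "If no change in biomarkers is demonstrated, correlations between baseline data for biomarkers and baseline data for clinical measures will be examined"

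The outcome list, headed "Biomarkers – change/baseline", names ten biomarkers. Seven clinical measures are listed, counting speckle tracking (STU) once. The participants are "The group of participants, who provided a blood sample at baseline", and their number is not given. Study 2 plans its change correlations without any such condition: "Correlations between change in GPS and change in performance-based tests will be examined".

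**The concern.** The two complementary conditions are most naturally read as alternatives, so that one set of correlations replaces the other. Three things are then wrong.

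1. **The gate tests the wrong quantity.** A paired test asks whether the mean or median change differs from zero. A marker that rises in some participants and falls in others can have zero mean change and still track clinical change closely. Conversely, a shift in the mean is no reason to set baseline associations aside.
2. **The branches answer different questions.** One concerns co-change over two weeks of treatment, the other cross-sectional association. The test result, not the objective, decides which is reported.
3. **The trigger is undefined.** Study 3 gives no alpha for a change being *demonstrated*, and does not say whether each, any or all of the ten biomarkers must show one. Two analysts could follow the text faithfully and produce different tables.

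At stake are real change associations that go unexamined when the average change is small, and baseline associations lost to a chance positive.

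**Working it through.** Study 3 states no sample size, power or alpha, so there is no figure of the plan's own to reproduce.

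**Inputs from the SAP.** Ten biomarkers and seven clinical measures (Study 3, Outcome measures); a cohort of 48 (Administrative Information), which is an upper limit for paired blood samples.

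**Assumptions not in the SAP.** Two-sided alpha 0.05 (the SAP states 0.05 only for the Study 2 sample size); n = 30 to 48 pairs; bivariate normal changes; gate = paired t-test p < 0.05; detection = Pearson p < 0.05.

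**Reading A: each biomarker has its own gate.** For normal data, the chance that a correlation is both examined and detected is close to

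P(gate opens) × P(correlation test significant).

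At n = 48, zero mean change and r = 0.5, this is 0.05 × 0.96 = 0.048. Simulation (40,000 trials per cell) gives:

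| n | true r | mean change 0 | 0.1 SD | 0.2 SD | 0.3 SD | 0.4 SD | no gate |
|---|---|---|---|---|---|---|---|
| 30 | 0.5 | 3.9% | 6.5% | 14.7% | 28.3% | 45.5% | 83% |
| 40 | 0.5 | 4.4% | 8.6% | 21.2% | 41.9% | 63.8% | 92% |
| 48 | 0.5 | 4.8% | 9.7% | 26.0% | 50.6% | 74.0% | 96% |
| 30 | 0.3 | 1.7% | 2.8% | 6.2% | 12.3% | 19.8% | 37% |
| 48 | 0.3 | 2.5% | 5.6% | 14.2% | 28.6% | 42.3% | 55% |

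In the other direction, a marker with no true mean change loses its baseline correlations to a false positive in 5% of trials.

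**Reading B: any one of the ten opens the gate for all.** With no true mean change and independent markers, P(gate opens) = 1 − 0.95^10 = 0.401. The same formula gives 0.096 at alpha 0.01 and 0.651 at alpha 0.10. With correlated markers at alpha 0.05 (20,000 trials per cell):

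| inter-marker correlation | gate opens by chance | r = 0.5 detected, n = 48 | r = 0.5 detected, n = 30 |
|---|---|---|---|
| 0 | 40% | 38.1% | 33.0% |
| 0.3 | 35% | 33.9% | 29.2% |
| 0.5 | 29% | 27.6% | 24.0% |

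Each time the gate opens by chance, all baseline correlations are dropped. With no true mean change, the choice of reading alone moves the chance of taking the change branch from 5% for a given marker to as much as 40% for the whole set.

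**Number of correlations.** 10 × 7 = 70 per set and 140 for both, or more if STU is split by muscle and load. If all are null, the expected nominal positives at 0.05 are 0.05 × 70 = 3.5 and 0.05 × 140 = 7.

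**The case against.** The strongest reply is that the plan does state a rule. Both branches are written down, and the gate is the change test rather than the correlations, so it cannot be used to pick the branch with the stronger association. That is fair: this is not free selection after seeing the correlations. But the trigger is left open, and a fully defined trigger would still test the wrong quantity.

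It can also be said that the text never forbids reporting the other set. Exclusivity is indeed a reading, though the natural one, and the figures above depend on it. A reader would probably assume 0.05 for alpha, but no convention supplies the unit of the gate.

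The parallel with Study 2 is limited. Study 2 hypothesises an association between changes, whereas either branch would meet Study 3's looser objective. It shows only that the plan does not treat a mean change as a general precondition for change correlations.

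The loss is confined to small and moderate mean changes. With r = 0.5 and n = 48, gated against ungated detection is about 89% against 96% at 0.5 SD. At n = 30 it is about 73% against 83% at 0.6 SD and 82% against 83% at 0.8 SD. The figures also give no credit for the baseline correlations reported when the gate stays shut, and Wilcoxon and Spearman were not simulated.

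Finally, a gate limits the number of comparisons, and the SAP calls these "four exploratory studies that originate from the initial trial registration". Both points bear on severity. Neither makes the paired test a sensible gate.

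**Conclusion.** The concern holds and should be fixed. Under the per-biomarker reading, the gate cuts detection of a true change correlation of 0.5 from 83–96% to 4–5% at zero mean change, 15–26% at 0.2 SD and 46–74% at 0.4 SD; above roughly 0.5 SD (n = 48) to 0.8 SD (n = 30) little is lost. Under the any-of-ten reading, chance alone discards every baseline correlation in 29–40% of trials for inter-marker correlations from 0.5 down to 0. The sizes rest on the stated assumptions about alpha, normality, number of pairs and strength of correlation. The logical point, that a test of average change says nothing about covariation of individual changes, needs none of them. The paired analysis of biomarker change itself is untouched.

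**What to change.** Delete both conditions in the Study 3 correlation section. State that baseline-with-baseline and change-with-change correlations are both estimated for all ten biomarkers, with 95% confidence intervals, whatever the paired tests show. Name one set as main in advance (for example change with change, which the section heading announces) and the other as supportive, and present both as exploratory.

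The cost is SAP wording and one more table from data already collected. The drawback is at least 140 correlations instead of 70, with about 7 instead of 3.5 nominal positives expected if all are null. They should therefore be read as estimates with intervals, not as tests.
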